### **2.4.8.2 Genetic variables**

Summary of BOR will be provided for the following patients:

- FcGR3A types: F/F, F/V, V/V and missing.
- HLA and KIR genotypes including:
  - HLA-B BW4-80lle+ and KIR3DL1+ vs HLA-B BW4-80lle- or KIR3DL1-.
  - KIR3DS1- vs KIR3DS1+.

### **2.4.8.3 Other variables**

Soluble CD38 will be summarized with descriptive statistics for responders/non-responders and listed.

In addition, graphs showing responder/non-responder rate by biomarker levels will be provided for the following parameters at baseline:

- Soluble CD38.
- Immune cell level (B-cell, T-cell and NK-cell subsets respectively in blood and bone marrow samples).

A listing of response data will be provided for patients with MRD.

## **2.4.9 Further therapy after discontinuation of investigational medicinal product administration during the study**

Further therapy for MM will be listed and not summary table will be provided.

## **2.5 DATA HANDLING CONVENTIONS**

### **2.5.1 General conventions**

For the data censored at detection limits, its value will be substituted by DL/2.

## 2.5.2 Data handling conventions for secondary efficacy variables

Not applicable

## 2.5.3 Missing data

For categorical variables, patients with missing data are not included in calculations of percentages unless otherwise specified. When relevant, the number of patients with missing data is presented.

### *Handling of disease characteristics missing/partial dates*

- If the day is missing, it will be estimated by 1.
- If the month is missing, it will be estimated by 1 (only for medical history variables).
- If the year is missing, no estimation will be performed.

### *Handling of medication missing/partial dates*

No imputation of medication start/end dates or times will be performed. If a medication date or time is missing or partially missing and it cannot be determined whether it was taken prior or concomitantly, it will be considered a prior, concomitant, and post-treatment medication.

For post anticancer treatments, if the anticancer treatment start date is missing, it will be imputed as follows:

1. If the anticancer treatment start day is missing and the anticancer treatment start month and year are the same as the study treatment end month and year, the anticancer treatment start day will be set equal to the date of last study treatment administration + 1.
2. If the anticancer treatment start day is missing and the anticancer treatment start month is not missing and the anticancer treatment start year is after the study treatment end year, the anticancer treatment start day will be set to 01.
3. If the anticancer treatment start day is missing and the anticancer treatment start month is after the study treatment end month and the anticancer treatment start year is the same as treatment end year, the anticancer treatment start day will be set to 01.
4. If the anticancer treatment start day and month are missing and the anticancer treatment start year is the same as study treatment end year, the anticancer treatment start date will be set equal to the date of last study treatment administration + 1
5. If the anticancer treatment start day and month are missing and the anticancer treatment start year is after the study treatment end year, the anticancer treatment start day and month will each be set to 01
6. If the anticancer treatment start day is missing and anticancer treatment start month is before the study treatment end month and the anticancer treatment start year is the same as treatment end year, the anticancer treatment start day will be set to 01

7. If the anticancer treatment start day, start month and start year is missing, the anticancer treatment start date will be set equal to the treatment end date + 1.

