PD	Increase of $\geq 25\%$ from lowest response value in any one of the following: 
Serum M-component (the absolute increase must be ≥ 0.5 g/dL) and/orUrine M-component (the absolute increase must be ≥ 200 mg/24 h) and/orOnly in patients without measurable serum and urine M-protein, the difference between involved and uninvolved FLC levels. The absolute increase must be >10 mg/dLOnly in patients without measurable serum and urine M-protein and without measurable disease by FLC levels, bone marrow plasma cell percentage (absolute % must be $\geq 10\%$)Definite development of new bone lesions or soft tissue plasmacytomas or definite increase in the size of existing bone lesions or soft tissue plasmacytomasDevelopment of hypercalcemia (corrected serum calcium >11.5 mg/dL) that can be attributed solely to the plasma cell proliferative disorder

All response categories (CR, sCR, VGPR, PR and PD) require two consecutive assessments made at any time before the institution of any new therapy; complete response and PR and SD categories also require no known evidence of progressive or new bone lesions if radiographic studies were performed. VGPR and CR categories require serum and urine studies regardless of whether disease at baseline was measurable in serum, urine both or either. Radiographic studies

are not required to satisfy these response requirements. Bone marrow assessments need not be confirmed. For progressive disease, serum M-component increases of ≥ 1 g/dL are sufficient to define response if starting M-component is ≥ 5 g/dL.

IMWG clarification for coding PD: Clarified that Bone marrow criteria for PD are to be used only in patients without measurable disease by M protein and by FLC levels. Clarified that 25% increase refers to M protein, FLC, and bone marrow results and does not refer to bone lesions, soft tissue plasmacytomas or hypercalcemia. Note the lowest response value does not need to be a confirmed value.

Table 10 - Additional response criteria for specific disease states

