##### ***Handling of medication missing/partial dates***

No imputation of medication start/end dates or times will be performed. If a medication date or time is missing or partially missing and it cannot be determined whether it was taken prior or concomitantly, it will be considered a prior, concomitant, and post-treatment medication.

For post anticancer treatments, if the anticancer treatment start date is missing, it will be imputed as follows:

1. If the anticancer treatment start day is missing and the anticancer treatment start month and year are the same as the study treatment end month and year, the anticancer treatment start day will be set equal to the date of last study treatment administration + 1.
2. If the anticancer treatment start day is missing and the anticancer treatment start month is not missing and the anticancer treatment start year is after the study treatment end year, the anticancer treatment start day will be set to 01.
3. If the anticancer treatment start day is missing and the anticancer treatment start month is after the study treatment end month and the anticancer treatment start year is the same as treatment end year, the anticancer treatment start day will be set to 01.
4. If the anticancer treatment start day and month are missing and the anticancer treatment start year is the same as study treatment end year, the anticancer treatment start date will be set equal to the date of last study treatment administration + 1.
5. If the anticancer treatment start day and month are missing and the anticancer treatment start year is after the study treatment end year, the anticancer treatment start day and month will each be set to 01.
6. If the anticancer treatment start day is missing and anticancer treatment start month is before the study treatment end month and the anticancer treatment start year is the same as treatment end year, the anticancer treatment start day will be set to 01.
7. If the anticancer treatment start day, start month and start year is missing, the anticancer treatment start date will be set equal to the treatment end date + 1.

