##### ***2.1.3.1 Primary efficacy endpoint(s)***

The primary efficacy endpoint is ORR, defined as the proportion of patients with sCR, CR, VGPR or PR as best overall response (BOR) as assessed by the IAC. The BOR will be derived using disease assessments performed from the start of treatment through the entire study excluding any assessments performed after the cutoff date or following the start of further therapies for MM.

The ordering of evaluations from best to worse is: sCR, CR, VGPR, PR, MR, stable disease (SD), progressive disease (PD), not evaluable (NE). BOR for patients without response assessment by the IAC will be 'Not evaluable'.

Subgroup analyses of BOR using IAC assessment will be performed for the variables listed in [Table 4](#).

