#### **2.1.3.2 Secondary efficacy endpoint(s)**

Secondary efficacy endpoints are defined below.

- Duration of Response (DOR) (in weeks): DOR is defined as the time from the date of the first IAC determined response ( $\geq$  PR) that is subsequently confirmed, to the date of first IAC determined PD or death, whichever happens earlier (if reported before the analysis cut-off date or the date of initiation of a new anticancer treatment). If progression and death are not observed before the analysis cut-off date or the date of initiation of new anticancer treatment, DOR will be censored at the earliest of the date of the last valid disease assessment not showing disease progression performed prior to initiation of a further anticancer treatment or the analysis cut-off date. DOR is determined only for patients who have achieved a confirmed response of  $\geq$ PR.
- Clinical benefit rate (CBR): defined as the proportion of patients with sCR, CR, VGPR, PR or MR as BOR according to IMWG criteria, as determined by the IAC.
- Progression free survival (PFS) (in months): defined as the time interval from the date of first isatuximab administration to the date of the first IAC-confirmed disease progression or the date of death due to any cause, whichever comes first. For patients who did not experience IAC-confirmed disease progression and death before the analysis cut-off date or the date of initiation of new anticancer treatment, PFS will be censored at the date of the last valid disease assessment not showing disease progression performed prior to initiation of a further anticancer treatment or the analysis cut-off date, whichever comes first.
- Overall survival (OS) (in months): defined as the time interval from the date of first isatuximab administration to death from any cause. In the absence of the confirmation of death before the cut-off date, OS will be censored at the cut-off date or at the last date the patient is known to be alive, whichever comes first.

- Time to response (TTR) (in weeks): TTR is defined as the time from first dose to first IAC response (PR or better) that is subsequently confirmed.
- Duration of follow-up (DFU) (in weeks): DFU is defined as the time from first dose to last response disease assessment before start of other therapy or cut-off date, whichever comes first.

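### The Phase 2 SAP imputes an incomplete start date of next anticancer therapy to the earliest possible day, ignoring any known progression date, so a real PFS event can become an earlier censored time

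*SAP*

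**What the plan says.** Phase 2 SAP 2.5.3, under the handling of missing or partial medication dates, gives seven rules for the start of post-study anticancer treatment. The Phase 1 SAP carries the same rules.

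- Day missing, same month and year as the end of study treatment (rule 1): "the anticancer treatment start day will be set equal to the date of last study treatment administration + 1".
- Day missing, later month or year (rules 2 and 3), or earlier month of the same year (rule 6): "the anticancer treatment start day will be set to 01".
- Day and month missing, same year (rule 4): "the anticancer treatment start date will be set equal to the date of last study treatment administration + 1". In a later year (rule 5), the date becomes 01 January.
- Whole date missing (rule 7): "the anticancer treatment start date will be set equal to the treatment end date + 1".

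The start of new therapy then limits the efficacy endpoints. In SAP 2.1.3.2, progression or death counts towards PFS or DOR only if it comes before that start. Otherwise PFS is "censored at the date of the last valid disease assessment not showing disease progression performed prior to initiation of a further anticancer treatment", and DOR is handled in the same way. In SAP 2.1.3.1, best overall response (BOR) is derived "excluding any assessments performed after the cutoff date or following the start of further therapies for MM". Protocol Appendix C says that response and progression categories "require two consecutive assessments made at any time before the institution of any new therapy".

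The SAP does not state that the imputed dates feed PFS and DOR, but no other use is evident: SAP 2.4.9 only lists further therapy. For adverse events, SAP 2.5.3 restricts imputed dates to categorisation. It sets no such restriction here.

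**The concern.** Subsequent therapy often follows progression, so the true order is often PD first and new therapy second. The rules choose the earliest date compatible with what was recorded and, apart from rule 6, with a start after the last dose. They never compare that date with a PD already in the database. If the imputed start lands on or before the PD date, the PD is no longer before new therapy and stops being an event.

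The schedule offers three routes to a PD dated after the last dose:

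- Day 1 assessments are done before dosing (Protocol 12.3.1). After Cycle 1, a Day 1 sample that stops treatment therefore falls about 14 days after the last dose.
- Myeloma tests are repeated at the end-of-treatment visit, 30 days after the last dose (12.4).
- Patients in PR or better who stop for reasons other than PD are assessed every 4 weeks off treatment (6.7.1, 12.5).

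For a patient who did progress first, the error acts in one direction on PFS: an event is replaced by a censored time about one assessment earlier. The second cut-off exists for the final time-to-event analysis (Protocol 6.7.2), so PFS is where this matters.

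**Working it through.** The plan gives no figure to reproduce: it states neither a rate of incomplete dates nor a PFS assumption.

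**Example (non-leap year).** Last dose 5 March (Day 15), PD sample 19 March (next Day 1), new therapy recorded as March with the day unknown. Rule 1 gives 6 March. PD on 19 March is then after new therapy, and PFS is censored at the previous Day 1, 19 February.

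**Share of events lost.** Inputs: the rules above (rule 6 excluded); last dose before the PD date; true start g days after PD, with g assumed. An event is lost if the imputed start is on or before PD.

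- *Only the day missing.* If PD and the new start share a calendar month, the imputed date is the 1st of that month or last dose + 1. Neither is later than PD, so the event is lost. If the start falls in a later month, the imputed date is the 1st of that month, after PD, so the event is kept. With a mean month of 365.25/12 = 30.44 days, the share lost is 1 - g/30.44, or 0 when g exceeds the month.
- *Day and month missing.* By the same reasoning, the event is lost if PD and start share a calendar year: 1 - g/365.25.
- *Whole date missing.* The imputed date is treatment end + 1, never later than PD: 100%.

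| g (days) | 7 | 14 | 21 | 28 | 42 |
|---|---|---|---|---|---|
| Day missing | 77% | 54% | 31% | 8% | 0% |
| Day and month missing | 98% | 96% | 94% | 92% | 89% |
| Whole date missing | 100% | 100% | 100% | 100% | 100% |

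Applying the rules to every calendar day over four years gives the same figures, whether the last dose is 14, 28 or 90 days before PD. If a tie between imputed start and PD is not counted as a loss, the first row becomes 74/51/28/5/0%.

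**PD dated on or before the last dose.** Rules 1-5 and 7 always give a date after the last dose, so 0% are lost outright. A later confirmatory sample can still fall on or after the imputed start. With the last dose on the first PD day, only the day missing, and therapy starting 1/7/14/21/28 days after confirmation, this happens in 97/77/54/31/8% of cases.

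**Effect on median PFS.** Simulation with N=33 (the lower end of the planned 33-36), exponential PFS with assumed medians of 3, 5 and 8 months, 28-day assessments, 20-32 months of follow-up and 400 runs per setting. Every event is treated as a PD dated after the last dose. The share lost among incomplete dates is 31%, 54%, 77% or 100%.

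| Dates incomplete | Events lost | Rise in average KM median (months) |
|---|---|---|
| 3% | 0.3-1.0 | 0.03-0.29 |
| 10% | 0.9-3.4 | 0.07-0.83 |
| 30% | 2.8-9.9 | 0.28-3.48 |

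For example, with an assumed median of 5 months, 10% incomplete and 54% of those lost, the average KM median moves from 5.69 to 5.94, a ratio of 1.044. As a rough check, under a constant hazard, turning a fraction d of events into censored times multiplies the median by 1/(1 - d). With d = 0.10 × 0.54 = 0.054 this is 1/0.946 = 1.057, of the same order.

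**The case against.** The strongest reply is that the conditions are narrow.

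- Myeloma tests fall on Day 1, which is a dosing day, and paraprotein PD needs a second sample. Dosing on or after the first PD sample is therefore plausible, and no event is then lost outright. This stands.
- A start 7 or 14 days after PD fits confirmed paraprotein PD only if the second sample was early, since Protocol 9.3.1 allows up to 4 weeks. At 28 days or more the day-only loss is 8% or less. This also stands, but PD by imaging, marrow or hypercalcaemia needs no confirmation, and the result for a missing month or whole date hardly depends on the gap.
- The start of new therapy is a scheduled collection item, so incomplete dates may be rare. The documents give no rate. At 3% the cost is at most about one event and 0.3 month.
- Loss through the confirmatory sample is only a possibility. The adjudication committee (IAC) works to its own charter, and nothing says that an imputed date overrides its determination.

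A reader might infer that the imputed date usually precedes PD. The documents do not support this, because it depends on where PD falls relative to the last dose and on which part of the date is missing. A reader might also infer that DOR is overstated. DOR events can be lost, but SAP 2.4.4.2 summarises DOR with descriptive statistics. An end date moved back to the previous assessment shortens the recorded duration, so the direction for DOR is undetermined.

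**Conclusion.** The point holds in a limited form. Followed as written, the rules can turn a documented PD into a time censored at the previous assessment when PD is dated after the last dose and the start of new therapy is incomplete. For patients who progressed first, this biases Kaplan-Meier PFS upward. With 10% of dates incomplete, the size is about 1-3 events and 0.1-0.8 month of median PFS. The upper ends assume that every PD is dated after the last dose. The missing-date rate, the gap to new therapy and the true median are all assumptions.

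The practical effect is on Phase 2 PFS. The Phase 1 SAP (2.4.4) summarises only BOR. PFS is a secondary, single-arm estimate without a hypothesis test. A reader might extend the point to a bias in favour of the primary endpoint, but the documents do not support that: an early imputed date can only remove assessments from BOR, which cannot raise ORR.

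**What to change.** In Phase 2 SAP 2.5.3:

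1. For PFS and DOR only, set the imputed start to the later of the current imputed date and the day after the IAC-determined PD, including its confirmatory sample, within the range that the recorded part of the date allows. If the recorded part shows that therapy began before PD, keep the current rule. If it allows a start after PD but not after confirmation, use the last day it allows.
2. Leave the BOR/ORR window as it is. A floor there, for instance at the last IAC assessment, could admit samples taken on rescue therapy.
3. State that imputed dates enter the PFS and DOR derivations, and report how many were imputed.
4. Add a sensitivity analysis that counts PD and death regardless of the new-therapy date.

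The floor at PD loses no event when PD came first and therapy started after the last dose. The current imputed date and the day after PD are then both no later than the true start, so the later of the two stays within the recorded range and after PD.

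The cost is SAP wording and a few lines of derivation code. The downside is that a few patients whose therapy truly began before PD would keep an event. The sensitivity analysis and the count of imputed dates would show how much this matters.

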### ***Handling of adverse events with missing/partial dates***

Missing or partial adverse event onset dates and times will be imputed so that if the partial adverse event onset date/time information or cycle/visit number does not indicate that the adverse event started prior to treatment or after the treatment-emergent adverse event period, the adverse event will be classified as treatment-emergent. No imputation of adverse event end dates/times will be performed. These data imputations are for categorization purpose only and will not be used in listings. No imputation is planned for date/time of adverse event resolution.

### ***Handling of adverse events with missing grade***

Missing grades, if any, will be included in the “all grades” category.

### ***Handling of missing assessment of relationship of adverse events to investigational medicinal product***

If the assessment of the relationship to isatuximab is missing, then the relationship to isatuximab has to be assumed and the adverse event considered as such in the frequency tables of possibly related adverse events, but no imputation should be done at the data level.

### ***Handling of potentially clinically significant abnormalities***

If a patient has a missing baseline he will be grouped in the category “normal/missing at baseline.”

For PCSAs with 2 conditions, one based on a change from baseline value or a normal range and the other on a threshold value, with the first condition being missing, the PCSA will be based only on the second condition.

Measurements flagged as invalid by the laboratory will not be summarized or taken into account in the computation of PCSA values.

Missing or partial adverse event onset dates and times will be imputed so that if the partial adverse event onset date/time information or cycle/visit number does not indicate that the adverse event started prior to treatment or after the treatment-emergent adverse event period, the adverse event will be classified as treatment-emergent. No imputation of adverse event end dates/times will be performed. These data imputations are for categorization purpose only and will not be used in listings. No imputation is planned for date/time of adverse event resolution.

#### **2.5.4 Windows for time points**

An episode occurred during a cycle if the date of sampling is after the first date of the cycle, but prior or equal to the first day of the next cycle.

#### **2.5.5 Unscheduled visits**

Unscheduled visit measurements of laboratory data and vital signs will be used for only computation of worst values and/or grades.

#### **2.5.6 Pooling of centers for statistical analyses**

Data from all sites will be pooled together for analyses.

#### **2.5.7 Statistical technical issues**

Not applicable.

### **3 INTERIM ANALYSIS**

Not applicable.

## 4 DATABASE LOCK

The database lock is planned to be twice in phase 2. The cut off for the first database lock is at approximately 4 months after last patient first dosed. The cut off for the second database lock is at approximately 12 months after last patient first dosed.

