--	---

	
Pharmacokinetics parameters will be summarized with descriptive statistics (mean, geometric mean, median, standard deviation, coefficient of variation, minimum and maximum).
 
Immune response, pharmacodynamics marker results will be descriptively summarized and tabulated.
 
Analysis of efficacy endpoints:
 
Best overall response will be listed along with relevant patient/disease characteristics as well as the secondary efficacy endpoints.
 
Primary analysis:
 
Analysis of efficacy endpoint will be performed on all patients who received at least one of the recommended dose across Phase I and II part:
 
ORR and a 95% two-sided confidence interval will be computed using Clopper-Pearson method. For recommended dose level, the null hypothesis that the true response rate (ORR) is <10% will be tested using a one-sided exact binomial test with a significance level of 0.025.
 
Secondary analysis:
 
The CBR will be analyzed using the same method as the primary efficacy analysis of ORR.
 
DOR, TTP, PFS and OS will be analyzed using Kaplan-Meier methods.
 
Analysis of the other exploratory endpoints:
 
The same analysis will be applied in Phase I and Phase II part.
 
The exploratory endpoints and the relationship to clinical outcomes will be analyzed with exploratory manner.
 
Planned database lock date:
 
The first cutoff date for the database lock is planned at approximately 4 months after last patient first dosed.
 
The second cutoff date for the database lock is planned at approximately 20 months after last patient first dosed.

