6.7.2 Determination of End of Clinical Trial (all patients)

The first analysis cutoff date for the statistical analysis for ORR will be 4 months after the date of the first dose of the last patient.

Second analysis cutoff date for the updated analysis of ORR and final analysis of time to events data will be 20 months after the date of the first dose of the last patient. Patients still on treatment at time of the second analysis cutoff date and who still continue benefiting from treatment with isatuximab will have the option to continue treatment under this protocol. Study will end after the completion of follow-up for all patients.

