Appendix J Protocol amendment history

The Protocol Amendment Summary of Changes Table for the current amendment is located directly before the Clinical Trial Summary.

AMENDED PROTOCOL 04 (14-Dec-2018)

OVERALL RATIONALE FOR THE AMENDMENT

The purpose of the second analysis is to obtain PFS and OS by monotherapy from mature data in Japanese patients. However, it was found only two events of OS in phase 2 at the first analysis, so 12 months would not be enough to observe median of OS. That median of OS in 20mg/kg arm in TED10893 P2S1 was 18.1 months. Therefore, second cut-off will be postponed from approximately 12 months to approximately 20 months.

Protocol amendment summary of changes table

Section # and Name	Description of Change	Brief Rationale
NAMES AND ADDRESSES OF	To delete information	These information are provided in CTP attachment.
CLINICAL TRIAL SUMMARY, 6.7.1 Duration of Study Participation for Each Patient	DURATION OF STUDY PERIOD (per patient) To add as follow; Patients with PR or better who come off treatment for reasons other than progression of disease will be followed for disease assessment every 4 weeks until progression or initiation of subsequent therapy, the second analysis cutoff date, whichever comes first.	To clarify follow-up assessment.
CLINICAL TRIAL SUMMARY, 6.7.2 Determination of End of Clinical Trial (all patients)	STATISTICAL CONSIDERATIONS Planned database lock - the second cutoff date: 20 months	To get enough period for observation of median of OS.
1.4 STUDY FLOWCHART - PHASE I PART	To add a new footnote as follow; Subsequent Cycles ^{3, 35}	To clarify assessment items post second analysis cut-off period.
1.5 STUDY FLOWCHART - PHASE II PART	To add a new footnote as follow; Subsequent Cycles ^{3, 35}	To clarify assessment items post second analysis cut-off period.
1.6 FOOTNOTES FOR STUDY FLOWCHARTS	33 To add as follow; "or second cut-off date, whichever comes first." To add as follow; 35. Post second analysis cut-off period, only AE/SAE reporting will be collected	To clarify study duration. To clarify assessment items post second analysis cut-off period.
1.7 PK FLOW CHART - PHASE I PART	To add a new footnote as follow; Subsequent Cycles ⁹	To clarify assessment items post second analysis cut-off period.

Section # and Name	Description of Change	Brief Rationale
	To add as follow; g Post second analysis cut-off period, only ADA samples will be collected.	To clarify assessment items post second analysis cut-off period.

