## 4 DATABASE LOCK

The database lock is planned to be locked twice after phase 2. The first is at approximately 4 months after last patient first dosed. The second is at approximately 12 months after last patient first dosed.

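### The Phase 2 SAP still dates the second cut-off at 12 months; the protocol moved it to 20 months because 12 was judged too short for median OS

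*SAP*

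**What the plan says.** - Phase 2 SAP, section 4 (Database lock): "The cut off for the second database lock is at approximately 12 months after last patient first dosed".
- Phase 1 SAP, section 4: "The second is at approximately 12 months after last patient first dosed".
- Protocol synopsis, planned database lock date: "The second cutoff date for the database lock is planned at approximately 20 months after last patient first dosed".
- Protocol 6.7.2, which also gives the purpose: "Second analysis cutoff date for the updated analysis of ORR and final analysis of time to events data will be 20 months".

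The reason for 20 months is in protocol Appendix J, under Amendment 04 (14-Dec-2018). The second analysis was meant to deliver mature PFS and OS. By the time of the first analysis two Phase 2 deaths had been recorded, and the sponsor concluded that "12 months would not be enough to observe median of OS". As a reference it gave a median OS of 18.1 months for TED10893 Phase 2 Stage 1 at 20 mg/kg. The cut-off was therefore moved from about 12 to about 20 months.

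Table 1 in section 1.5 of each SAP records changes to the protocol's statistical section. In both SAPs it lists Amendment 1 only. Section 1.6 of the Phase 2 SAP says that the document is the first version.

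**The concern.** Two current documents give two dates for one analysis, and the date drives results. In the Phase 2 SAP the cut-off closes the window for best overall response (2.1.3.1) and sets the censoring of DOR, PFS and OS (2.1.3.2). OS and PFS then go into Kaplan-Meier quartiles, including the median, and into survival probabilities every 4 months (2.4.4.2). None of those sections gives a number of months; only section 4 does. A programmer working from the SAP would apply 12 months.

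The final OS, PFS and DOR would then be reported at a time the sponsor has called insufficient, and median OS might not be estimable. There is also a question of integrity. The cut-off was changed after the first analysis of an open-label trial. With two dates on file, the reported estimates could follow either, so a single documented date is needed.

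**Working it through.** **Comparison of the texts.** The 20-month figure is a planning choice with no stated formula, so there is nothing to reproduce.

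| Source | Second cut-off after last patient's first dose |
|---|---|
| Protocol synopsis | about 20 months |
| Protocol 6.7.2 | 20 months |
| Phase 2 SAP section 4 | about 12 months |
| Phase 1 SAP section 4 | about 12 months |

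The gap is 20 − 12 = 8 months. It lies between current texts; Appendix J is used only for the reason. The reference median of 18.1 months falls between the two dates.

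**Inputs for the size of the effect.** From the documents: median OS 18.1 months (Appendix J) and N = 33, the lower end of the planned 33-36 (protocol 13.1). Assumed: exponential survival, uniform accrual and no dropout. The documents do not give the length of accrual, so a range is shown.

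**Step 1. Patients with minimum follow-up only.** The expected proportion dead at t months is 1 − 2^(−t/18.1).
- t = 12: 1 − 2^(−12/18.1) = 0.368, and 33 × 0.368 = 12.2 deaths.
- t = 20: 1 − 2^(−20/18.1) = 0.535, and 33 × 0.535 = 17.7 deaths.

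If all 33 patients had only this follow-up, the binomial probability that at least 17 have died is 0.060 at 12 months and 0.658 at 20.

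**Step 2. Allowing for accrual.** With accrual over a months, cut-off f and λ = ln 2/18.1, the expected proportion dead is 1 − [e^(−λf) − e^(−λ(f+a))]/(λa).

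| Accrual a (months) | Dead at f = 12 | Dead at f = 20 |
|---|---|---|
| 0 | 36.8% | 53.5% |
| 6 | 43.6% | 58.5% |
| 12 | 49.4% | 62.7% |
| 18 | 54.4% | 66.4% |

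At 12 months the expected proportion stays below one half for accrual up to 12 months, and passes it only modestly for 18. At 20 months it exceeds one half for every accrual length tried.

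**Step 3. Is the Kaplan-Meier median reached?** Trials of 33 patients were simulated under the same model, counting those in which the estimated survival curve falls to 0.5 by the cut-off. Repeat runs agree to within about three percentage points.

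| Accrual (months) | Reached, 12-month cut-off | Reached, 20-month cut-off |
|---|---|---|
| 6 | 43% | 89% |
| 12 | 74% | 96% |
| 15 | 84% | 98% |

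**The case against.** The strongest reply is that this is a matter of document order, not a rival plan. Amendment 04 was written after the first analysis. The Phase 2 SAP is a first version that lists only Amendment 1, so it probably matched the protocol then in force. Its date is not visible in the supplied text, and a later version or addendum cannot be ruled out. The SAP also asks to be read together with the protocol, its endpoint definitions refer to a cut-off without naming a month, and protocol follow-up already runs to the second cut-off. It is the protocol, not the SAP, that calls the second analysis the final one for time-to-event data: "final analysis of time to events data will be 20 months after the date of the first dose of the last patient". Finally, both documents agree on the 4-month primary ORR analysis, and the endpoints affected are descriptive single-arm summaries without a test.

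Most of this is fair, and it limits the consequence. It does not remove the conflict: the only date in the SAP is the superseded one, and no alignment is recorded in the supplied text.

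The objections to the numbers also carry weight:

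- The 6% against 66% contrast in Step 1 assumes instantaneous accrual. That cannot hold, because the pooled set includes Phase I patients treated before Phase II opened. Step 3 is the better guide, and with 15 months of accrual the median is usually reached even at 12 months.
- The 18.1-month exponential model fits the early data poorly. For an assumed 30 Phase 2 patients it predicts 4.3, 7.0 or 9.4 deaths at the 4-month cut-off for accrual of 0, 6 or 12 months, against two observed. The probability of two or fewer is 0.18, 0.017 and 0.001.
- If median OS were 24 months, the chance of reaching the median at 20 months would fall to 56-85% for accrual of 6 to 15 months. The same simulation gives 16-55% at 12 months, so the levels move but the direction does not.
- Only OS was modelled. No size is claimed for PFS, DOR or best response.

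**Conclusion.** The concern holds. The Phase 2 SAP, as written, sets the second cut-off 8 months earlier than the current protocol, at a date the sponsor rejected for this purpose. The conflict is a matter of text and needs no assumption. Its effect on median OS does: under exponential survival with an 18.1-month median, uniform accrual over 6 to 15 months and no dropout, the chance of reaching the Kaplan-Meier median is 43-84% at 12 months and 89-98% at 20. These figures show the direction and rough scale; they are not a precise effect size. The primary ORR result is not affected. The final OS, PFS and DOR estimates and the updated ORR are, so the date must be corrected before the second lock.

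**What to change.** In section 4 of the Phase 2 SAP, replace the second cut-off with approximately 20 months after the last patient's first dose, in line with protocol 6.7.2. Add Amendment 04 to Table 1 with its date and reason. State in sections 2.1.3 and 2.4.4 that final OS, PFS and DOR, and the updated best overall response and ORR, use this cut-off. If an updated SAP or addendum already exists, cite it.

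Make the same change to section 4 and Table 1 of the Phase 1 SAP for consistency. It alters no Phase 1 time-to-event summary, because section 2.4.4 there summarises best response only and adds one plasma-cell listing.

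The cost is SAP wording. The protocol already plans survival follow-up, and disease follow-up of responders who stop treatment without progression, to the second cut-off (6.7.1 and 12.5-12.6), so no further data collection is needed.
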